8.2 CLASSIFICATION OF AN ADVERSE EVENT

8.2.1 SEVERITY OF EVENT

The severity of each adverse event must be recorded as 1 of the choices on the following scale:

Mild	No limitation of usual activities
Moderate	Some limitation of usual activities
Severe	Inability to carry out usual activities

An AE that is assessed as severe should not be confused with a SAE.

8.2.2 RELATIONSHIP TO STUDY PROTOCOL

Each reported AE will be described by its duration (i.e., start and end dates), regulatory seriousness criteria if applicable, and suspected relationship to study protocol in accordance with definitions set forth at each IRB. In general, these relationships are categorized as likely, possible, unlikely and not related. Experience teaches that gray zone instances will arise, and the site coordinators and PIs will be trained to adjudicate possible SAEs in a systematic fashion. To ensure consistency of SAE causality assessments, investigators will apply the following general guideline:

Yes - There is a plausible temporal relationship between the onset of the AE and administration of the study protocol and the AE cannot be readily explained by the subject's clinical state, inter-current illness, or concomitant therapies; and/or the AE follows a known pattern of response to study drug or the AE abates or resolves upon discontinuation of study drug;

No - Evidence exists that the AE has an etiology other than the study protocol (e.g., preexisting medical condition, underlying disease, inter-current illness, or concomitant medication); and/or the AE has no plausible temporal relationship to the study drug.

Adjudication of each AE will proceed as follows: First, the coordinator will consult the site PI to review the chart. Next, the PI will contact members of the clinical care team to clarify uncertainty related to inadequate documentation. Third, if the PI is unable to decide for certain if an AE or SAE occurred, he or she will have the option of sending a personal health identifier-stripped, written narrative of the event to the other site PIs who will vote up or down as to whether the event constituted an AE or SAE.

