2.3 POTENTIAL RISKS AND BENEFITS

2.3.1 KNOWN POTENTIAL RISKS

Patients will only receive current usual care for acute heart failure. There will be no experimental drugs or therapies. However, the SSU will receive protocolized care while the usual care arm will receive the non-protocolized AHF care per routine. Past small studies and retrospective analyses demonstrate the safety and efficacy of SSU management. Furthermore, if SSU treated patients are not ready for discharge, they will be admitted. Thus, there is a built in 'safety-net.' However, the SSU strategy has not been tested in a randomized, controlled, clinical trial. Nevertheless, there is a risk that patients will be discharged prematurely from either setting.

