8.4.2 SERIOUS ADVERSE EVENT REPORTING

All SAE's will be reviewed within 48 hours and all AE's within 7 days of discovery. SAE's will be followed through the entire follow up period (i.e. through day 30). Any SAE discovery will be reported to the DCC who will then report to the DSMB. If placebo treated patient, standard reporting to the IRB will occur. If active treated patient, and deemed to be related to drug, the SAE will be reported to the DSMB chair within 7 business days by email, fax, or phone of any fatal or life-threatening adverse event that is unexpected.

15 Calendar Day Written Report

The Investigator will also be required to notify the IRBs and all participating investigators, in a written Safety Report, of any serious, unexpected AE that is considered reasonably or possibly related to the strategy-of-care arm

72 hour reporting

For the discovery of an unexpected serious adverse event thought to be related to study procedures the Investigator(s) will notify the Chair of the DSMB by email within 72 hours.

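### The Yes/No causality guideline in section 8.2.2 is worded for a study drug and steers worsening heart failure or death after early SSU discharge toward *No*, and it does not match the scale that the 15-day report relies on

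*Combined protocol and SAP*

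**What the plan says.** Section 8.2.2 contains two causality schemes.

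- **Four levels.** Relationship to the study protocol follows each IRB's definitions, and in general "these relationships are categorized as likely, possible, unlikely and not related".
- **Yes/No.** "To ensure consistency of SAE causality assessments, investigators will apply the following general guideline". *Yes* requires plausible timing and that "the AE cannot be readily explained by the subject's clinical state, inter-current illness, or concomitant therapies". A second route to *Yes* is worded only for a drug trial: "and/or the AE follows a known pattern of response to study drug or the AE abates or resolves upon discontinuation of study drug". The *No* branch applies where "Evidence exists that the AE has an etiology other than the study protocol (e.g., preexisting medical condition, underlying disease", among other examples, or where timing relative to a study drug is implausible.

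Section 2.3.1 states "There will be no experimental drugs or therapies". It also accepts, for both arms, that "there is a risk that patients will be discharged prematurely from either setting".

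Section 8.4.2 makes the expedited reports depend on relatedness. The 15-day written report to IRBs and participating investigators is required "of any serious, unexpected AE that is considered reasonably or possibly related to the strategy-of-care arm". The 72-hour notice to the DSMB chair needs an unexpected SAE thought related to study procedures. A 7-business-day report to the DSMB chair refers to active-treated patients and relation to a drug.

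Section 8.2.3 exempts a long list of heart failure signs and treatments from regulatory reporting, with an exception for events attributable to spironolactone.

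**The concern.** The intervention is a care setting and a shorter stay. If it does harm, for example through discharge before the patient is ready, the harm will show itself as progression of the disease the patient already has. A causality test that sets underlying disease against the study protocol, as if only one could be responsible, suits a drug with its own toxicity. It does not suit a strategy that would act through the disease.

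Two things are at stake. The first is the investigator's case-level judgment of whether the strategy contributed. The second is the set of expedited reports that depend on that judgment and go to IRBs, other investigators and the DSMB chair. With two unmapped scales, two sites could also code the same event differently while both follow section 8.2.2.

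**Working it through.** No arithmetic applies, because the point depends on no rate, effect size or sample size. The check traces one case through the text: a patient discharged early from the SSU who, within the AE reporting period, has a serious worsening of heart failure, or dies.

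1. **Timing.** The event follows soon after protocol care, so the timing condition for *Yes* is met.
2. **First limb of *Yes* (section 8.2.2).** The event must not be readily explained by the patient's clinical state. Section 5.1 requires both an AHF diagnosis and previous heart failure, so that explanation is available for every participant. Read at face value, the limb fails.
3. **Second limb of *Yes*.** It requires a known response to a study drug, or resolution when the drug is stopped. Section 2.3.1 says there is no experimental drug, so this limb has nothing to act on.
4. ***No* branch.** Underlying disease and preexisting condition are its leading examples. The wording fits the event.
5. **Result under Yes/No.** The guideline points to *No*.
6. **Result under the four-level scale.** An investigator may record *possible*. That meets the relatedness part of the 15-day trigger; Yes/No has no such category. Nothing in section 8.2.2 says which scheme governs reporting.
7. **Expectedness.** The 15-day and 72-hour reports also need the event to be unexpected. The section 8.2.3 list includes dyspnea, hypoxemia, mechanical ventilation and escalation of heart failure therapy. Its only exception names spironolactone, which is not the intervention. For these events, correcting section 8.2.2 alone would not produce a report. Death and cardiac arrest are not on the list, so for them the causality judgment can be the deciding step.
8. **7-business-day report.** It is tied to relation to a drug, and on its wording it cannot be triggered here.
9. **Possible repairs elsewhere.** The vote among site investigators in section 8.2.2 settles whether an AE or SAE occurred, not its cause. Section 10.4.5 rules out an adjudication committee.
10. **What does not depend on causality.** Section 8.4.2 sends every SAE to the DCC and then to the DSMB. Section 8.1.2 lists cardiac arrest and intubation or positive pressure ventilation as reportable SAEs in the SSU arm. Sections 8.1, 8.4.1 and 10.4.4 treat death, re-hospitalization and ED visits as safety measures, with follow-up to 90 days, and section 10.4.3.1 tests death or re-hospitalization between arms.

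**The case against.** The strongest reply is that the Yes/No text is only a general guideline, set beside a scale that allows *possible*. *No* also needs evidence of a cause other than the study protocol, and an early SSU discharge is itself protocol care. Whether an event is readily explained is a judgment, and adherence to the discharge criteria is recorded before discharge (section 7.3.7), which gives investigators something to judge by. Sections 8.1.1 and 8.1.2 already contemplate complications of the protocol. This stands to the extent that a reader should not infer that such events will always be scored *No*, or that the count of related events will be near zero whatever the truth. The text does not compel either result, and section 10.4.4 plans no summary restricted to related events.

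The reply does not remove the defect. The guideline exists to make SAE causality consistent, and an investigator has to set its wording aside to reach *possible*.

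A second reply is that premature-discharge harm resembles the disease, so comparison between arms is the informative signal, and the plan has it. This is right. A reader might infer that the DSMB would not see these events, but the causality-independent route to the DSMB rules that out. The DSMB also judges on all the data it reviews (section 10.4.7) and receives SSU admission rates at enrollment milestones (section 10.4.3.1).

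Third, the DSMB Charter and the IRB definitions are separate documents not available here. They could narrow the gap, but they would not change the conflicting text in the protocol.

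**Conclusion.** The point holds in a limited form. Applied as written, the Yes/No guideline steers the harm named in section 2.3.1 toward *No*, and it conflicts with the four-level scale that the 15-day trigger presupposes. The exposure is loss of case-level attribution and of expedited related-SAE reports, mainly for events outside the section 8.2.3 list, such as death or cardiac arrest. Overall safety surveillance and the primary analysis are not affected.

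The documents give no basis for a count of affected events. The readmission rates in section 2.2 might tempt a reader to produce one. They are 30-day readmissions from a retrospective study, not SAEs caused by premature discharge. General AE reporting here runs for 5 days after randomization, and re-hospitalization is captured separately as an outcome.

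The conclusion assumes that investigators follow the guideline's wording and that no document outside the protocol overrides it.

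**What to change.** Change the three sections together, since section 8.2.2 alone would leave the other barriers in place.

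- **Section 8.2.2.** Keep only the four-level scale, with one trial-wide definition checked against the local IRB definitions. Suggested text: *Likely or possible: the assigned setting, the timing of discharge or transfer, or SSU-protocol care plausibly contributed to the event, even if heart failure is the proximate cause.* Delete the study-drug criteria.
- **Section 8.4.2.** State that *likely* and *possible* both count as related for every expedited report. Replace the placebo and drug triggers with wording that refers to the strategy of care.
- **Section 8.2.3.** Replace the spironolactone exception with one that refers to the strategy of care. Reconcile the exemption of mechanical ventilation with its listing as a reportable SAE for SSU patients in section 8.1.2.
- **Section 10.4.4.** State that all SAEs will be compared by arm regardless of attribution, and that this comparison is the main safety signal.

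The cost is a protocol wording change, site training and somewhat more possibly related reports. The trial is unblinded (section 10.6.1), so attribution to the strategy may differ by arm. That is why attribution should supplement the all-SAE comparison and not replace it.

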8.2.3 EXPECTEDNESS

The following signs, symptoms, observations and events are frequently observed in association with acute heart failure and its treatments and are exempted from regulatory reporting (including, but not limited to local IRB) unless known to be caused by, or plausibly caused by spironolactone: dyspnea, orthopnea, paroxysmal nocturnal dyspnea, chest pain, fever, hypoxemia, rapid pulse, rapid respiratory rate, dizziness, syncope, altered mental status, confusion, anxiety, generalized weakness, anorexia, nausea, abdominal pain, back pain, early satiety, vomiting, pneumonia, acute renal failure, repleting potassium, skin infection, cancer, surgery not related to treatment of pulmonary embolism, electrocardiography abnormalities (atrial arrhythmias, ventricular dysrhythmias, right bundle branch block, and ST and T wave changes), elevated troponin level, elevated BNP or NT ProBNP level, high white blood cell count, pulmonary infiltrate, pleural effusion, cardiomegaly, electrolyte imbalances, need for oxygen therapy, need for vasopressor support, need for blood product transfusion, need for mechanical ventilation (invasive or non-invasive), need for physical or occupational therapy, need for analgesia, need for skilled nursing facility upon discharge, need for early follow up with physician, escalation of heart failure therapy, need for cardiac catheterization or PA line placement, need for sleep study.

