6 STUDY AGENT

6.1 STUDY AGENT(S) AND CONTROL DESCRIPTION

This study will test a strategy-of-care, SSU AHF management for less than 24 hours vs. usual care (hospitalization) for lower risk AHF patients who are planned to be admitted. Only therapies commonly utilized during usual AHF care will be applied. For example, , IV loop diuretics, and topical and oral vasodilators. Usual care will be at the discretion of the clinical care team. No drugs or therapies that are not approved by the FDA will be allowed.

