8.1.2 DEFINITION OF SERIOUS ADVERSE EVENTS (SAE)

An AE will be classified as an SAE if:

- It results in death (i.e., the AE actually causes or leads to death).
- It is life threatening (i.e., the AE, in the view of the investigator, places the subject at immediate risk of death. It does not include an AE that, had it occurred in a more severe form, might have caused death).
- It requires or prolongs inpatient hospitalization. Admission from the SSU itself does not count as an SAE, but an expected outcome. However, if in the investigators judgment, admission from the SSU was due to some other complication of the study protocol, rather than an expected outcome, it should be reported as an SAE

SPECIFIC REPORTABLE SAE for SSU/OU arm patients:

- Cardiac arrest

- Need for intubation or positive pressure ventilation
- It results in persistent or significant disability/incapacity (i.e., the AE results in substantial disruption of the subject's ability to conduct normal life functions).
- It is considered a significant medical event by the investigator based on medical judgment (e.g., may jeopardize the subject or may require medical/surgical intervention to prevent one of the outcomes listed above).

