8.4 REPORTING PROCEDURES

8.4.1 ADVERSE EVENT REPORTING

The study period during which AEs must be reported begins after informed consent is obtained and initiation of study treatment and for 5 days after randomization. Patients will be followed out to 90 days for death, ED utilization, and re-hospitalization as part of the study outcomes, which will also count as safety measures. Subject's hospital discharge summaries will be examined at hospital discharge and all non-exempt AEs will be investigated by examining necessary medical records.

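### The reporting exemption in section 8.2.3 is lifted only for events caused by spironolactone, so listed events caused by the SSU strategy can escape IRB reporting, and ventilation sits on both the exempt and the reportable list

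*Combined protocol and SAP*

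**What the plan says.** Section 8.2.3 (Expectedness) lists events that are common in acute heart failure and its treatment. It says that they "are exempted from regulatory reporting (including, but not limited to local IRB") and adds one exception: "unless known to be caused by, or plausibly caused by spironolactone". The list includes "need for mechanical ventilation (invasive or non-invasive"), and also vasopressor support, acute renal failure, syncope and electrolyte imbalance.

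Section 8.1.2 (definition of SAEs) has a block headed "SPECIFIC REPORTABLE SAE for SSU/OU arm patients". One of its entries is "Need for intubation or positive pressure ventilation".

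Section 8.4.1 says that discharge summaries will be checked and that "all non-exempt AEs will be investigated by examining necessary medical records".

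On what is being tested, section 6.1 states: "This study will test a strategy-of-care, SSU AHF management for less than 24 hours vs. usual care (hospitalization"). Section 2.3.1 adds: "There will be no experimental drugs or therapies".

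**The concern.** An exemption for expected events normally has a safeguard: if the study intervention may have caused the event, it is reported after all. Here the safeguard names a drug that the trial does not test. It therefore does nothing for the exposure that the trial does assign, namely protocol-driven care in a short stay unit.

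The listed events include ones that could plausibly follow from that exposure. Section 5.2 excludes patients who need ventilatory or vasopressor support at ED disposition, so a later need is a new deterioration. Section 8.1.1 counts complications of protocol-mandated interventions as adverse events, so the protocol means to capture them. Section 8.2.3 then takes the listed ones out of IRB reporting, whatever their relation to the strategy.

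Ventilation adds a second problem. A site with a ventilated SSU patient finds the event named as reportable in one section and exempt in another. The protocol does not tell the site how to combine the two, and sites could resolve this differently.

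**Working it through.** No arithmetic applies. The check follows one event through every rule that could govern it: an SSU-arm patient needs ventilation, and the investigator thinks that the SSU strategy may have caused it.

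| Section | Condition in the rule | Result for this event |
|---|---|---|
| 8.1.2 | Named SAE, SSU/OU arm | Reportable; recipient not stated |
| 8.2.3 | On the list; exception only for spironolactone | Exempt from regulatory and IRB reporting |
| 8.4.1 | Non-exempt AEs only | Record examination not promised by this section |
| 8.4.2, general rule | Any SAE | Goes to the DCC, then the DSMB; reviewed within 48 hours |
| 8.4.2, 15-day report to IRBs and investigators | Serious, unexpected, possibly related to the strategy arm | Not triggered if listed events count as expected |
| 8.4.2, 72-hour notice to the DSMB chair | Unexpected SAE, related to study procedures | Not triggered, for the same reason |
| 8.4.2, 7-business-day notice to the DSMB chair | Active-treated patient, related to drug, unexpected | Written for a drug trial; does not map onto these arms |
| 8.2.2 and 8.3 | Each AE | Site chart review and CRF recording remain |

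Four things follow.

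1. *The exception names the wrong intervention.* Outside section 8.2.3 the body text does not mention spironolactone. Its drug class appears only in section 10.1.1, as one of the guideline-adherence measures.
2. *The related-event rules do not close the gap.* They refer to the strategy or to study procedures, as they should, but both require the event to be unexpected. Section 8.2.3 is the only place where the protocol says which events are to be expected.
3. *The overlap is real but limited.* Section 8.1.2 names two clinical events for the SSU arm, cardiac arrest and ventilation. Only ventilation is also on the exempt list.
4. *The two lists differ in scope.* The named SAEs apply to the SSU arm, while the exemption applies to both arms.

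The wording looks carried over from a drug trial. Sections 8.2.2 and 8.3 refer to a study drug, and section 8.4.2 makes standard IRB reporting depend on the patient being placebo treated. That origin is an inference, and the point does not depend on it.

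**The case against.** The strongest reply is that the exemption is narrower than it looks. It concerns regulatory reporting, not recording, review or the DSMB. Section 8.4.2 sends any SAE to the DCC and on to the DSMB with no condition on expectedness. Section 8.2.2 starts adjudication of each AE with a chart review, and section 8.3 requires each AE to be recorded on the CRF. Section 8.1.1 gives an upgrade from the SSU to intensive care as an example of an AE. Section 8.1.2 asks for an SAE report when admission from the SSU was due to a complication of the study protocol. On this view sections 8.1.2 and 8.2.3 are compatible: ventilation goes to the DCC and DSMB, and only the IRB report is waived.

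Much of this stands, and it rules out three stronger readings.

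- A reader might infer that sites may neither investigate nor report a ventilated SSU patient. The rules just cited contradict that. Section 8.4.1 limits what it promises to investigate; it forbids nothing.
- A reader might infer that the DSMB will see incomplete data. The documents do not show this, and the DSMB charter, to which sections 8.5 and 8.6 defer, is a separate document that is not included here.
- A reader might infer that the spironolactone exception can never operate. Patients may receive the drug as ordinary care, since its class is a guideline measure. The exception is misdirected, not shown to be empty.

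The reply does not supply an exception for strategy-caused events in section 8.2.3. Nor does the protocol state the split between DSMB and IRB on which the compatible reading relies.

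**Conclusion.** The point holds for IRB and other regulatory reporting and for expedited notice to the DSMB chair. Followed as written, the protocol leaves a listed event caused by the SSU strategy exempt from the first and outside the second. For ventilation in the SSU arm, the recipient of the report and the governing list are both unstated.

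The conclusion rests on one assumption: that an event listed under Expectedness is treated as expected when the 15-day and 72-hour rules are applied. The protocol does not say so outright, but it gives no other definition. If a site judged a listed event unexpected in a particular patient, the 15-day and 72-hour rules could still apply.

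The size cannot be given as a number, because the documents contain no rates for these events. The primary analysis and the sample size are not affected. The correction is still worth making: the trial is unblinded (section 10.6.1), and section 10.4.7 sets no formal stopping rules and leaves early halting to the DSMB's judgement on safety, so clear and uniform reporting carries weight.

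**What to change.** - In section 8.2.3, replace spironolactone with the assigned strategy of care or study procedures, so that the exemption lifts for events that either may have caused.
- Reconcile sections 8.1.2, 8.2.3, 8.4.1 and 8.4.2. State to whom an event on both lists is reported (DCC, DSMB, IRB), and that a specific reportable SAE is not exempt from investigation under section 8.4.1.
- In section 8.4.2, say whether a listed event judged related to the strategy falls under the 15-day and 72-hour rules, and reword the placebo, active-treatment and drug conditions to match the two arms.

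The named SAE list need not be identical in the two arms, but the text should make clear which rules apply to which arm.

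The cost is a short protocol amendment, a memo to sites and a few more events to review.
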